## SECTION I: RESEARCH PLAN

### 1. Statement of Purpose:

State the scientific aim(s) of the study, or the hypotheses to be tested.

We plan to conduct a randomized, controlled trial to determine the impact of the Apple Watch Series 6 on both patient-reported outcomes and clinical utilization over 1 year. Our research method will employ a patient-centered health data-sharing platform (called Hugo) for real-world surveillance of outcomes in 150 total patients after they receive direct current cardioversion (DCCV) or catheter ablation for treatment of atrial fibrillation or atrial flutter. We will recruit a total of 150 patients across 3 clinical sites- 60 at Yale-New Haven Hospital, 60 at the Mayo Clinic, and 30 at Duke Health- before they undergo DCCV for atrial fibrillation or atrial flutter or after they undergo catheter ablation for atrial fibrillation or atrial flutter. Half of the patients will be randomized to receive the Apple Watch Series 6, while half will receive a control device (Withings Move). Patients will then be queried about specific symptoms related to atrial fibrillation and medication adherence monthly for a total of 6 times post-procedure (6 months) and also at 12 months. This project will provide novel and needed post-market data about the recently cleared Apple Watch Series 6 ECG and irregular rhythm detection notification features and, on a larger scale, help delineate the impact of an innovative digital health technology on real-world patient outcomes.

**Specific Aim 1:** To assess the impact of using the Apple Watch ECG and irregular rhythm notification features on patient-reported outcomes and clinical utilization after patients receive cardioversion or catheter ablation for atrial fibrillation or atrial flutter.

**Specific Aim 2:** To determine the accuracy of the Apple Watch ECG compared to physician interpretation of 12-lead ECGs obtained in routine clinical care.

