#### Overall Study Design

This will be a prospective multi-center, randomized, controlled trial of 150 patients conducted to assess the impact of individual use of the Apple Watch on patient-reported and clinical outcomes at 1 year. Sixty of these patients will be recruited at Yale-New Haven Hospital. This sample size was calculated assuming 80% power to detect an effect size of 8.8 on the AFEQT questionnaire (slightly higher than the minimal clinically important difference of 5), with alpha 0.05. Additionally, we will validate Apple Watch Series 6 ECG readings when a simultaneous 12-lead ECG is obtained in clinical practice; the purpose of this validation is to assess the Apple Watch's ability to serve as a heart rate and ECG monitoring tool that may be used for periodic rhythm checks in post-market surveillance of other medical products (such as catheters used for atrial fibrillation ablation or antiarrhythmic medications).

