Of note, even though the Apple Watch Series 6 device is not intended for use in individuals previously diagnosed with atrial fibrillation, the ECG feature is not recommended for users with arrhythmias *except* for atrial fibrillation and sinus rhythm (since the software can only distinguish these two heart rhythms). People with atrial fibrillation may be more likely to purchase this device than others to monitor their rhythm and correlate with symptoms. Indeed, in the Apple Heart Study, nearly 20% of first study visit participants reported a diagnosis of atrial fibrillation/flutter before enrollment, even though a history of atrial fibrillation was an exclusion criterion. Few digital health studies have enrolled patients with clinical morbidities to examine outcomes; such studies have instead focused on healthy volunteers. Our study will address this limitation. Additionally, a study examining the impact of the Apple Watch on patient-reported outcomes and clinical utilization requires an enriched population; otherwise, study duration would be many years with a population size multiples larger than our proposal, resulting in significant cost and delays in generating much-needed evidence.

For patients undergoing cardioversion, if there is time before the cardioversion and always after the cardioversion, we will ask the patient to obtain an ECG using the Apple Watch Series 6 (and the RA will assist the patient if needed), with the 10-second interval that has the best resolution and is free from artifact for comparison to the interpretation of a 12-lead ECG obtained for clinical care (as these are 10 seconds long). If possible, we will also ask the patient to take a SpO2 reading while the RA is present and they are connected to a standard, medical grade pulse oximeter in the clinical setting.

A separate survey, both for patients undergoing cardioversion and who received catheter ablation for atrial fibrillation or flutter, will be sent at enrollment asking patients, only with the help of study staff, to enter both their Apple Watch pulse oximeter reading and the reading taken using a medical grade SpO2 monitor.

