### **Secondary Clinical Outcomes**

1. Change within individual domains of AFEQT questionnaire (symptoms, daily activities, treatment concern, and treatment satisfaction) monthly (at 1, 2, 3, 4, 5, and 6 months as well as at 12 months)
2. Additional clinical treatment for atrial fibrillation or flutter at 6 and 12 months: a composite outcome of rhythm control intervention, which is defined as at least one additional cardioversion, initiation of antiarrhythmic medical therapy, dose escalation of antiarrhythmic medication, change to another antiarrhythmic medication, or ablation for atrial fibrillation or flutter. The medication data will be obtained primarily from electronic health record data.
3. Acute care use at 6 and 12 months: emergency department visits, observation stays, all hospitalizations
4. Outpatient care use at 6 and 12 months: outpatient primary care visits, outpatient cardiology or cardiac electrophysiology visits, and scheduled telephone encounters.
5. Rhythm-related diagnostic testing at 6 and 12 months: total ECGs and total outpatient heart rhythm monitors
6. Anticoagulation persistence: through adopting the Brief Medication Questionnaire and asking patients if they have taken their anticoagulant, and for how many days in the past 1 week (monthly at 1, 2, 3, 4, 5, and 6 months as well as at 12 months)

For the primary outcome, we will calculate the difference in the AFEQT global questionnaire score at baseline and 6 months and perform a comparison between the patients randomized to the Apple Watch and patients randomized to Withings Move.

The secondary clinical utilization outcomes will be compared between the two groups. Data obtained through Hugo will be used to obtain most outcomes. Electronic health records will be used to review ECG tracings. We will also trend patients' monthly responses about anticoagulation adherence.

The secondary outcomes for accuracy of Apple Watch Software Features that will be compared are a comparison of the heart rhythm (identical to 12-lead ECG or different), rate (difference in beats per minute), and intervals: PR, QRS, and QT interval (difference in milliseconds) between what is assessed by the Apple Watch ECG feature and 12-lead ECGs during hospitalization or outpatient follow-up. This will be a blinded independent assessment of the Apple Watch ECG, and we will calculate both inter-observer reliability (among two reading cardiologists of Apple Watch ECGs), as well as intra-observer reliability.

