### 1.6.2 SECONDARY ENDPOINT ANALYSIS

The secondary clinical utilization outcomes will be compared between the two groups. Data obtained through Hugo will be used to obtain most outcomes. As these will intended to be composite outcomes, we will use the t-test or the Wilcoxon rank-sum test for comparison between the Apple Watch and Withings arms.

We will also use the t-test for comparison of the individual domains of the AFEQT questionnaire.

Electronic health records will be used to review ECG tracings. We will also trend patients' monthly responses about anticoagulation adherence. These analyses will be conducted for the entire studied population.

The secondary outcomes for accuracy of Apple Watch Software Features that will be compared are a comparison of the heart rhythm (identical to 12-lead ECG or different), rate (difference in beats per minute), and intervals: PR, QRS, and QT interval (difference in milliseconds) between what is assessed by the Apple Watch ECG feature and 12-lead ECGs during hospitalization or outpatient follow-up. Inter-observer and intra-observer agreement in assessment of the Apple Watch ECGs will be assessed using intraclass correlation coefficient (ICC).

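### Aim 2 asks for accuracy, but rhythm is scored only as identical or different: add an AF cross-table with sensitivity and specificity

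*SAP*

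**What the plan says.** - **Aim.** Specific Aim 2 (Protocol, Section I.1) is "To determine the accuracy of the Apple Watch ECG compared to physician interpretation of 12-lead ECGs obtained in routine clinical care". Overall Study Design adds that "we will validate Apple Watch Series 6 ECG readings when a simultaneous 12-lead ECG is obtained in clinical practice", with the purpose of judging whether the watch can serve for periodic checks of rhythm when other products are under surveillance.
- **Rhythm outcome.** SAP 1.6.2 defines it as "a comparison of the heart rhythm (identical to 12-lead ECG or different". SAP 1.1, the protocol's Secondary Clinical Outcomes and Statistical Considerations (Section I.12) give the same definition. Rate and the PR, QRS and QT intervals are compared as differences.
- **What is scored.** SAP 1.6.2 labels the outcome as accuracy of software features and describes the comparison as "between what is assessed by the Apple Watch ECG feature and 12-lead ECGs". The protocol's Secondary Clinical Outcomes gives the same list and then says "This will be a blinded independent assessment of the Apple Watch ECG", with "inter-observer reliability (among two reading cardiologists of Apple Watch ECGs" to be calculated.
- **When tracings are taken.** For cardioversion patients, Enrollment Procedure says "if there is time before the cardioversion and always after the cardioversion, we will ask the patient to obtain an ECG". Follow-Up asks for a watch ECG at every routine clinical ECG.
- **Reader agreement.** SAP 1.6.2: "Inter-observer and intra-observer agreement in assessment of the Apple Watch ECGs will be assessed using intraclass correlation coefficient (ICC".

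**The concern.** A rhythm check can fail in two ways: it can miss AF, or it can call AF when there is none. The protocol's own risk section (Section I.9) lists these as separate device risks, although they are not Aim 2 endpoints. An identical/different score counts both as the same event. Its natural summary, a percentage identical, therefore cannot show how often AF was missed, which is what a user of the watch for rhythm surveillance most needs to know.

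The percentage also depends on how many of the paired tracings show AF. Part of that mix is set by clinic workflow, because the tracing before cardioversion is taken only when time allows.

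Two wording points add to this. The SAP can be read as scoring the software label although the protocol points to cardiologist readers. And ICC is the only reader-agreement statistic named, without a statement of whether it covers rhythm.

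**Working it through.** **Is accuracy planned elsewhere?** No. Neither document mentions AF sensitivity, AF specificity, a cross-table or kappa. SAP 1.1's general rule gives categorical data as median with interquartile range, which yields no accuracy figure for a yes/no variable. Irregular rhythm notifications are only counted.

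**Is there a plan figure to reproduce?** Not for Aim 2. The total of 150 concerns AFEQT only. With difference 8.8, SD 18.5, two-sided alpha 0.05 and 80% power it needs 70 per arm, or 140, and 140/0.92 = 153 with 8% drop-out, close to 150.

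**What a percentage identical can hide.** Inputs: 150 patients at 1:1 give 75 in the watch arm. One pair per patient and the AF share are my assumptions. Identical = (AF detected + non-AF correctly called) / 75. In each row the two accuracy profiles give the same percentage.

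| AF / non-AF pairs | Identical | Profile A: sens / spec | Profile B: sens / spec | Watch that never detects AF |
|---|---|---|---|---|
| 8 / 67 | 71/75 = 94.7% | 50% / 100% | 100% / 94.0% | 67/75 = 89.3% |
| 15 / 60 | 68/75 = 90.7% | 53.3% / 100% | 100% / 88.3% | 60/75 = 80.0% |
| 22 / 53 | 64/75 = 85.3% | 50% / 100% | 100% / 79.2% | 53/75 = 70.7% |
| 38 / 37 | 56/75 = 74.7% | 50% / 100% | 100% / 48.6% | 37/75 = 49.3% |

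In the second row, A is (8 + 60)/75 and B is (15 + 53)/75.

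**Dependence on the rhythm mix.** Take cardioversion-day tracings only. Let f be the share of patients with a pre-procedure tracing (all assumed AF) and r = 10% the assumed AF share afterwards. AF share p = (f + r)/(1 + f), and identical = p × sens + (1 − p) × spec. For f = 0, 25%, 50% and 100%, p = 10%, 28%, 40% and 55%.

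| Assumed sens / spec | Identical at those four shares |
|---|---|
| 60% / 98% | 94%, 87%, 83%, 77% |
| 95% / 98% | 98%, 97%, 97%, 96% |
| 90% / 90% | 90% throughout |

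Now add two follow-up pairs per patient at 20% AF (assumed). At f = 0, p = (0.1 + 0.4)/3 = 16.7%; at f = 100%, p = (1 + 0.1 + 0.4)/4 = 37.5%. The 60%/98% watch then scores 92% and 84%, and a 90%/98% watch 97% and 95%.

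**Flutter.** Flutter patients are eligible (Section I.7), and Enrollment Procedure says the software separates only AF and sinus rhythm. If the software label were scored, every flutter pair would count as different, so flutter shares of 5%, 10% or 20% (assumed) would cap the percentage at 95%, 90% or 80%. A cardiologist reading has no such cap.

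**ICC.** In an illustrative two-category table of two readers, with rows (80, 6) and (7, 37), kappa and ICC are both 0.78. In an illustrative three-category table (sinus, AF, flutter) with rows (70, 2, 1), (2, 28, 6) and (1, 6, 14), kappa is 0.76. ICC is then 0.84 to 0.85 under four of the six numeric codings and 0.51 under the two that place sinus between AF and flutter.

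**The case against.** Identical/different is a variable recorded for each pair, not a declared summary. Scoring a pair requires both rhythms to be known, so a cross-table can be built from the same data. This stands: a reader might infer that the planned data cannot yield sensitivity, and that is not so. The gap is that nobody has planned to report it, so the handling of flutter and the choice of reading would be settled after the results are in view. It also means the measure needs an addition, not removal.

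A reader might infer that workflow alone could move the result from 94% to 77%. The documents do not support that as an expected size. It needs an assumed 60%/98% watch, cardioversion-day tracings only, and pre-procedure capture running from none to all. Ablation patients enrol on the day after their procedure, so the timing issue does not touch them, and follow-up pairs dilute it further.

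A reader might also infer that the software label is what will be scored, so that flutter forces mismatches. The protocol points the other way: it names cardiologist readers, selects the best artifact-free segment for comparison, and describes review of tracings (Section IV). Only a clarification is needed.

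Finally, a reader might conclude that ICC is wrong here. The SAP does not say that it covers rhythm. It suits rate and intervals, and it does no harm for a two-category rhythm.

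**Conclusion.** The point holds as a cheap improvement to a secondary aim. Aim 2 asks for accuracy, and the one planned rhythm measure cannot by itself distinguish missed AF from false AF. With 15 AF pairs among an assumed 75, the same 90.7% covers sensitivity anywhere from 53% to 100%. The documents give no AF share, flutter share, number of pairs or expected accuracy, so every size here is illustrative; the merging of the two errors does not depend on those values. The mix effect is real but depends on assumptions, and it is small or nil when sensitivity and specificity are close. The choice of scored reading and the agreement statistic are one-line clarifications. Nothing here touches the AFEQT analysis or the sample size.

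**What to change.** In SAP 1.6.2:

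1. Keep the identical/different measure and add a cross-table of watch rhythm against 12-lead rhythm, with flutter and unclassifiable tracings shown separately.
2. Report AF sensitivity and specificity with 95% intervals that allow for repeated tracings per patient.
3. State that the scored watch rhythm is the blinded cardiologist reading, how disagreement between the two readers is settled, and that the software label is reported separately where it is retained. No section says that the label is recorded as data.
4. If reader agreement on rhythm is reported, use kappa; keep ICC for rate and intervals.

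The cost is SAP wording and modest extra analysis of tracings already planned. The downside is a possibly less favourable figure, and an imprecise sensitivity if few AF tracings are paired: for example, 16 of 20 detected gives an exact 95% interval of 56% to 94%. That imprecision exists either way, and a percentage identical would hide it.
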